- We hypothesize that LCC warnings at 30% size that include an image (i.e., pictorial warnings) will decrease willingness to use LCCs, compared with FDA-proposed text-only LCC warnings at 30% size and Surgeon General text-only warnings at 10% size.
- We hypothesize that LCC warnings at 30% size that include an image (i.e., pictorial warnings) will increase cognitive elaboration, knowledge of LCC harms, beliefs about LCC harms, and negative affect compared with FDA-proposed text-only LCC warnings at 30% size and Surgeon General text-only warnings at 10% size.
- We hypothesize that LCC warnings at 30% size that include an image (i.e., pictorial warnings) will decrease LCC susceptibility, past 7 day little cigar use, and past 7 day cigarillo use compared with FDA-proposed text-only LCC warnings at 30% size and Surgeon General text-only warnings at 10% size.

Trial Design

The study is designed to be a parallel group trial, with participants evenly allocated to each study condition, using a superiority framework.

Methods: Participants, Interventions, and Outcomes

Methods Overview

We will conduct a one-week web-based RCT among U.S. youth who are susceptible to, have ever used, or currently use LCCs. In this study, LCC warnings on packs will be electronically presented to participants daily to determine if pictorial LCC warnings at 30% size decrease willingness to use LCCs compared to FDA proposed text-only warnings at 30% size and a control condition (Surgeon General text-only warnings at 10% size). We will apply a daily diary methodology to present LCC warnings on packs to participants over time. Qualtrics will contact, screen, consent and administer the survey. To enroll participants, Qualtrics will screen participants using our inclusion criteria and measures and invite eligible participants to enroll in the study. To collect at least 700 quality completes, we anticipate enrolling up to 2,100 people.

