At the beginning of the baseline survey (day 1), participants will first consent to participate in the study and then complete a questionnaire about their LCC use and susceptibility, exposure to cigar advertising and warnings, and demographic characteristics, in addition to other measures. At the end of the baseline questionnaire, survey software will randomly assign participants to one of the 3 study conditions. The three study conditions are 1) Pictorial (text + image) 30% size warnings , 2) FDA-proposed text-only LCC warnings at 30% size, and 3) Control condition (current status Surgeon General text-only warnings at 10% size). Participants will be contacted each day and invited to complete the survey for that day of the study protocol.

For six subsequent days (days 2-7), participants will be contacted and asked to complete a daily survey. During these daily surveys, participants will view an image of a cigarillo package with a warning according to the participant's condition. Participants will view a total of 6 different warnings over the course of 6 days. Before seeing the warning, participants will be asked about how often they have thought about the health risks of smoking cigars. After seeing the warning, participants will be asked about the appeal of the cigars in the package, how relevant they feel the warning is to their lives, and how worried the warning makes them feel. Participants will also be asked whether they saw any warnings outside the study about the harms of cigar use in the past day.

For the post-test on day 8, participants will be asked to complete a questionnaire about their willingness to use LCCs, LCC use, and susceptibility among other measures.

Participant timeline

Potential participants will be invited to complete the screener (Day 0) and those who are eligible will be invited to participate in the study. On Day 1, eligible participants will be asked to complete a baseline survey. The baseline survey will be open to enrollment for 2 days. After the baseline closes, participants will receive a survey every morning for Days 2-7 that includes an LCC warning and questions about their cognitive elaboration over the previous day, reactions to the warning, and warning exposure over the previous day. Participants will also be asked to complete a final post-test survey on Day 8.

Survey timing:

Study Setting

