The study will be conducted with online surveys, so participants can complete the surveys from any location. Participants must reside in the United States (US) to meet eligibility criteria.

Participants

Eligibility criteria for participation in this study:

1. Members of the recruitment panel (we are partnering with a panel provider for recruitment of all participants)
2. Agree to provide their honest answers
3. Susceptible to using LCCs, or have ever used little cigars and/or cigarillos, or currently use little cigar and/or cigarillos in the past 30 days
4. Age 15 – 20 years old
5. Currently living in US or a US territory
6. Inclusion criteria based on the design of the study:
 - a. Able to complete 2 surveys that take approximately 10 minutes
 - b. Able to complete a 2-minute survey each day for 6 days
7. Inclusion criteria based on verifying real participants:
 - a. Able to verify they are not a bot using CAPTCHA
 - b. Able to answer a simple, random math question

Interventions

Experimental Conditions

- 1) FDA-proposed warnings with added images at 30% size (pictorial warnings)
- 2) FDA-proposed text-only LCC warnings at 30% size
- 3) Control condition – Surgeon General text-only warnings at 10% size

Warning Stimuli

The stimuli will vary based on the day of the protocol. The packages that the study warning labels will be shown on will be standardized across the three conditions (see table below for warning text). Specifically, warning labels will be shown on cigarillo packages that are red and branded with the fictitious name “Grey Fox” to minimize the influence of brand loyalty and pre-existing brand perceptions.

Stimuli Order

Day	Condition 1	Condition 2	Condition 3
Day 2	WARNING: Tobacco use increases the risk of infertility, stillbirth and low birth weight.	WARNING: Tobacco use increases the risk of infertility, stillbirth and low birth weight.	SURGEON GENERAL WARNING: Tobacco Use Increases The Risk Of Infertility, Stillbirth And Low Birth Weight.
Day 3	WARNING: This product contains nicotine. Nicotine is an addictive chemical.	WARNING: This product contains nicotine. Nicotine is an addictive chemical.	SURGEON GENERAL WARNING: This Product Contains Nicotine. Nicotine Is An Addictive Chemical.

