Day 4	WARNING: Cigar smoking can cause cancers of the mouth and throat, even if you do not inhale.	WARNING: Cigar smoking can cause cancers of the mouth and throat, even if you do not inhale.	SURGEON GENERAL WARNING: Cigar Smoking Can Cause Cancers Of The Mouth And Throat, Even If You Do Not Inhale.
Day 5	WARNING: Cigars are not a safe alternative to cigarettes.	WARNING: Cigars are not a safe alternative to cigarettes.	SURGEON GENERAL WARNING: Cigars Are Not A Safe Alternative To Cigarettes.
Day 6	WARNING: Cigar smoking can cause lung cancer and heart disease.	WARNING: Cigar smoking can cause lung cancer and heart disease.	SURGEON GENERAL WARNING: Cigar Smoking Can Cause Lung Cancer And Heart Disease.
Day 7	WARNING: Tobacco smoke increases the risk of lung cancer and heart disease, even in nonsmokers.	WARNING: Tobacco smoke increases the risk of lung cancer and heart disease, even in nonsmokers.	SURGEON GENERAL WARNING: Tobacco Smoke Increases The Risk Of Lung Cancer And Heart Disease, Even In Nonsmokers.

Additional intervention details

Participants can withdraw from the study at any time if they choose to do so by no longer responding to the survey links and may withdraw their data by contacting the UNC study team.

Multiple strategies have been implemented to maximize adherence to the trial protocol, including reaching out to participants with invitations and reminders each day.

There is no relevant concomitant care or interventions that are permitted or prohibited during the trial.

Outcomes

Primary

- Willingness to use LCCs (day 8)

- Average willingness to use score measured by survey, measured with 2 questions. The final willingness to use score is a mean of the response to the 2 questions, on a scale of 1 to 5, where 1 indicates low willingness to use LCCs and 5 indicates a high willingness to use LCCs.

Secondary

- Past 7 day little cigar use (day 8)
 - Measured by survey with 1 item
- Past 7 day cigarillo use (day 8)
 - Measured by survey with 1 item
- LCC susceptibility (day 8)
 - Measured by survey with 3 items
- Cognitive elaboration about risk of LCC use (day 8)
 - Measured by survey with 1 item
- Warning negative affect/worry (each day)
 - Measured by survey with 1 item
- Knowledge of LCC harms (day 8)
 - Measured by survey with 13 items
- Beliefs about LCC harms (day 8)
 - Measured by survey with 10 items

Other

- LCC quit intentions (day 8)
 - Measured by survey with 3 items
- Past 7 day use of other tobacco products (day 8)

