Qualtrics will manage participant incentives. Participants in studies conducted by Qualtrics receive an incentive based on the length of the survey and their specific profile. The types of rewards vary and may include cash, airline miles, gift cards, redeemable points, sweepstakes entrance and vouchers. For this study, participants who complete the baseline, 3 of the daily message surveys, and the post survey on day 8 will receive an incentive. Participants who complete only a few of the surveys but do not satisfy the criteria above will not receive an incentive.

Methods: Assignment of interventions

Allocation and Blinding

Participants will not be informed specifically about the possible interventions that they may be assigned to. Researchers will not be blinded to the condition that participants have been assigned to. All outcome measures will be assessed via online survey. At the end of the baseline survey, survey software will randomly assign participants to one of the three study arms. Participants will have an equal chance of being randomized to each study arm.

Methods: Data collection management, and analysis

Data collection methods

Data collection will be conducted using Qualtrics web survey platform. Where possible, the measures used are previously developed and validated measures. Multiple strategies have been implemented to maximize adherence to the trial protocol, including reaching out to participants with invitations and reminders each day, and compensating them based on completion of the most important questionnaires (i.e., baseline, at least 3 daily surveys, and the post survey).

Screener

Qualtrics will invite potential participants to complete the screening survey and people who are eligible will be invited to complete the baseline survey. The screener is used to assess participant eligibility and collect demographic data.

Baseline Survey: Day 1

- Eligible participants will be invited to participate in the study and complete the baseline survey to enroll. The baseline survey will be open to enrollment for 2 days.
- The first part of the baseline survey will be an assent/consent form with an agreement to participate in the study.

- The baseline survey contains baseline tobacco use and susceptibility questions and additional demographic questions.
- At the end of the baseline questionnaire, survey software will randomly assign participants to one of the 3 study conditions.

Daily Surveys: Days 2-7

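### Willingness to use LCCs, the primary outcome, is not named among the Day 1 measures or as a model covariate, which costs precision and weakens the missing-data assumption but does not invalidate the comparison

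*Combined protocol and SAP*

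**What the plan says.** All references are to the combined protocol and SAP.

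- **Outcome.** The Outcomes section lists willingness as the primary outcome at Day 8: "The final willingness to use score is a mean of the response to the 2 questions, on a scale of 1 to 5".
- **Baseline content.** There are two descriptions. Under Data collection methods (Baseline Survey: Day 1): "The baseline survey contains baseline tobacco use and susceptibility questions and additional demographic questions". In the Methods Overview, participants "complete a questionnaire about their LCC use and susceptibility, exposure to cigar advertising and warnings, and demographic characteristics, in addition to other measures". Neither names willingness, but the second ends with an open reference to further measures.
- **Post-test content.** On Day 8, "participants will be asked to complete a questionnaire about their willingness to use LCCs, LCC use, and susceptibility among other measures". Here willingness is named.
- **Hypothesis.** Pictorial warnings "will decrease willingness to use LCCs, compared with FDA-proposed text-only LCC warnings at 30% size and Surgeon General text-only warnings at 10% size".
- **Population.** Eligibility covers people who are "Susceptible to using LCCs, or have ever used little cigars and/or cigarillos, or currently use little cigar and/or cigarillos in the past 30 days".
- **Analysis.** Statistical Methods gives a linear model for Day 8 willingness with assigned condition as the only named predictor. Covariates are mentioned as the means of handling missing outcomes under a missing-at-random (MAR) assumption, but none is named.
- **Size.** The Sample Size section gives 700 people, 233 per group, 80% power, alpha 0.05 and d = 0.26 for pictorial against FDA text-only. The Methods Overview expects to enrol up to 2,100 to obtain at least 700 usable completes.

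**The concern.** Participants range from people who have never used LCCs but are susceptible to current users, so starting willingness can be expected to differ widely between them. A person's own score a week earlier is a natural predictor of the Day 8 score. The trial already has a survey before randomisation, and it already asks about susceptibility, a secondary outcome that is measured again on Day 8. The plan does not say that its two primary items are asked there, and it commits to no baseline term in the model.

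Two things are at stake. The first is precision: any variance that baseline willingness would explain stays in the error term. The second is missing data. Randomisation takes place at the end of the baseline survey, so loss before Day 8 is loss after randomisation. With a single Day 8 outcome, maximum likelihood draws on the observed outcomes and the covariates in the model, so the MAR assumption is only as good as those covariates. Without baseline willingness, nobody can check directly whether completers in each arm started equally willing.

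**Working it through.** **Inputs.** From Sample Size: d = 0.26 (SD = 1 on the standardised scale), 233 per group, alpha 0.05, power 80%. From the Methods Overview: up to 2,100 enrolled for at least 700 completes. The correlation ρ between baseline and Day 8 willingness is not in the documents, so 0.3 to 0.7 is assumed.

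**Step 1: reproduce the plan's figure.** For a two-sided, unadjusted comparison of two means,

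n per group = 2(1.960 + 0.842)² / 0.26² = 232.3, rounded up to 233; three arms give 699.

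Power at 233: the standard error is √(2/233) = 0.0926, so 0.26/0.0926 = 2.806, and Φ(2.806 − 1.960) = 80.1%. An exact t-test calculation gives 79.97%. A one-sided test would need only 183 per group. The plan's figure is therefore two-sided and uses no baseline adjustment.

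**Step 2: adjust for baseline willingness.** The residual SD becomes √(1 − ρ²), and power = Φ(2.806/√(1 − ρ²) − 1.960). For ρ = 0.5: 2.806/0.866 = 3.240, and Φ(1.280) = 90.0%.

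| Assumed ρ | Residual SD | Power at 233 per arm | n per arm for 80% | Detectable d at 80% |
|---|---|---|---|---|
| none | 1.000 | 80.1% | 233 | 0.260 |
| 0.3 | 0.954 | 83.7% | 212 | 0.248 |
| 0.4 | 0.917 | 86.5% | 196 | 0.238 |
| 0.5 | 0.866 | 90.0% | 175 | 0.225 |
| 0.6 | 0.800 | 93.9% | 149 | 0.208 |
| 0.7 | 0.714 | 97.6% | 119 | 0.185 |

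**Step 3: allow for what is already collected.** Suppose baseline use and susceptibility were in the model and explained an assumed 25% of the variance. Power would then be about 90% (the same residual SD as ρ = 0.5). Adding baseline willingness so that 36–49% is explained gives about 94–97.5%. The gain is 4 to 8 percentage points, not 4 to 18.

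**Step 4: chance imbalance.** The standard error of a chance difference in mean baseline willingness between two arms is 0.093 SD, a 95% range of about ±0.18 SD. The unadjusted standard error already includes this. It is noise, not bias.

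**Step 5: loss after randomisation.** If 2,100 were enrolled and 700 gave usable data, 1,400/2,100 = 67% would lack a usable Day 8 outcome. As an illustration with assumed values, suppose pictorial-arm completers had started 0.1 SD less willing than completers in the comparison arm, with ρ = 0.6. The unadjusted Day 8 contrast would shift by 0.1 × 0.6 = 0.06 SD, which is 0.06/0.26 = 23% of the planned effect. The documents give no sign that this will happen. The point is that the plan, as written, could not detect it directly.

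**The case against.** The strongest reply has four parts.

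**Absence is not proven.** A reader might infer that willingness is not measured on Day 1. The documents do not support that. The Methods Overview leaves the baseline list open and the questionnaire is not included. The Day 8 label in Outcomes does not settle it either, because susceptibility carries the same label and is asked at baseline. This stands: the accurate statement is that willingness is not named.

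**The hypothesis needs no starting level.** A reader might infer that a decrease cannot be judged without each person's first score. The hypothesis is a comparison with the other two conditions in a parallel-group trial with equal allocation. Randomisation makes that Day 8 contrast valid, and the plan meets its own power target unadjusted. This also stands.

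**The gain may be modest.** The plan already foresees covariates and already collects use and susceptibility, which also allow completers and dropouts to be compared on related measures. This stands in part: Step 3 shows a smaller gain, but the plan does not commit to those covariates.

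**Asking twice may have a cost.** Participants may repeat their Day 1 answers, which would shrink the between-arm difference in every arm comparison. A shrinkage of 1 − √(1 − ρ²), that is 8%, 13%, 20% or 29% at ρ = 0.4, 0.5, 0.6 or 0.7, would cancel the whole gain over an unadjusted analysis. The documents give no evidence on whether this would occur. It is a real downside, but closely related use and susceptibility questions are already asked on Day 1, and the plan does not give priming as a reason for leaving willingness out.

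**Conclusion.** The point holds as one about precision and missing data. Willingness is not named among the Day 1 measures, and the Day 8 model names no baseline term. The primary contrast remains valid and has its stated 80% power. Adjusting for baseline willingness would raise that power to about 84–98% for assumed correlations of 0.3–0.7. If use and susceptibility already explained 25% of the variance, the rise would be from about 90% to 94–97.5%. These figures hold d at 0.26 and assume no shrinkage from repeated answering.

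The missing-data argument adds weight, because up to two-thirds of those enrolled may lack usable Day 8 data and the MAR covariates are unnamed. Its size cannot be estimated from the documents. A reader might also infer that most Day 8 variation is stable difference between people. That is plausible in so mixed a sample, but the documents give no figure for it, and the conclusion does not need it.

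**What to change.** 1. State whether the two willingness items are asked on Day 1. If not, add them to the baseline survey before randomisation.
2. Pre-specify the baseline mean score as a covariate in the Day 8 linear model, and name it among the covariates on which the MAR assumption rests.
3. Report baseline willingness by arm for completers and non-completers.
4. If the items cannot be added, or participants have already passed baseline without them, pre-specify baseline LCC susceptibility and use status as covariates. These are already collected, so this needs only analysis text.

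The cost is two items in a survey of about 10 minutes, a sentence or two of analysis text, an entry in the amendment table and, under the plan's own rule on changes to participant interaction, IRB approval. The remaining downside is possible consistent answering on Day 8, which could slightly shrink the between-arm difference.

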
Protocol Amendment History

Version	Date	Description of Change	Brief Rationale
1	6/26/2024	Original protocol finalized	
2	8/28/2024	Protocol updated to reflect that baseline may be open for 2 days	Allows eligible potential participants more time to enroll in the study
